7.7.7.3 Severity

The principal investigator or sub-investigator will judge the severity of adverse events in accordance with the below definitions. The highest severity of each event during its period of occurrence will be recorded as the severity in the CRF.

- Mild: Signs or symptoms are found, but activities of daily life are not disturbed.
- Moderate: Activities of daily life are disturbed due to discomfort, and/or abnormality is clinically demonstrated.
- Severe: Activities of daily life are impossible, and/or major clinical effects are demonstrated.

7.7.7.4 Causal relationship with study drug

The principal investigator or sub-investigator will judge the causal relationship with the study drug in accordance with the following criteria:

- Not related: The adverse event can be clearly explained by a factor other than the study drug, and/or there is no valid chronological relationship between the study drug and the adverse event.
- Possibly related: The adverse event may have been caused by a factor other than the study drug, but a causal relationship with the study drug cannot be ruled out.

- Probably related: It is unlikely that the adverse event was caused by a factor other than the study drug.
- Related: There is a valid chronological relationship between administration of the study drug and onset of the adverse event, and the event cannot be explained by a factor other than the study drug

Adverse events judged to be “Possibly related”, “Probably related” or “Related” are taken to be adverse drug reactions.

7.7.7.5 Predictable adverse drug reactions

Adverse drug reactions listed in the most recent investigator’s brochure for duloxetine, or in any reports about adverse drug reactions submitted separately to the IRB, study site, or the principal investigator, are taken to be predictable adverse drug reactions.

7.7.7.6 Adverse events of special concern

7.7.7.6.1 Suicide-related adverse events

The duloxetine package insert, includes, as drug-class labeling, the following requirement to take great care: “There have been reports of increases in the risks of suicidal ideation and suicidal planning in patients aged under 24 administered antidepressants, so consideration should be given to the risk/benefit relationship when this drug is to be administered”. Therefore, the principal investigator or sub-investigator will evaluate any suicidal thinking using the C-SSRS questionnaire, as detailed in Section 7.7.2 , and will record any suicide-related adverse events.

The principal investigator or sub-investigator will perform sufficient monitoring of subjects who suffer from adverse events that are clearly or possibly suicide-related.

If a subject suffers a suicide-related adverse event, and/or if requested by the sponsor, the principal investigator will report the details of the relevant adverse event to the sponsor, by fax, email or telephone, or orally. After the sponsor has received the relevant information, he/she will promptly request the Safety Evaluation Committee to perform a review. If necessary, the sponsor can also request the principal investigator to provide additional information.

7.7.7.7 Adverse events such as laboratory test results

The principal investigator or sub-investigator will judge whether or not any changes from the baseline by laboratory test results (hematology, blood chemistry, and urinalysis) and abnormalities in other safety endpoints (e.g. examination findings, body weight, blood pressure, pulse rate, ECG findings) are clinically significant. Laboratory test results that deviate from the reference range will be handled as abnormal values.

If a baseline value is abnormal, but worsens after study initiation, the principal investigator or sub-investigator will judge whether or not this is clinically significant. Events judged by the principal investigator or sub-investigator to be clinically significant will be recorded as adverse events. When an

abnormal test result is accompanied by disease or other toxicity, the disease name and/or details of toxicity will be reported as an adverse event.

An event will be considered clinically significant if one or more of the following criteria is met, and judgment about clinical significance in other situations will be at the discretion of the principal investigator or sub-investigator:

- The criterion for a serious adverse event is met (refer to Section 7.7.7.8).
- Study drug discontinuation or dose reduction is required.
- Drug administration or another procedure is required for treatment.
- An additional test or other medical procedure is required.
- Management of abnormal hepatic function test results is necessary, and the discontinuation criteria (Appendix 2) are met.

If management of abnormal hepatic function test results is necessary, and the discontinuation criteria (Appendix 2) are met, evaluation and additional assessment will be performed, and records will be made in the follow-up assessment form for abnormal hepatic function.

7.7.7.8 Serious adverse events

7.7.7.8.1 Definition

Of the adverse events observed after study initiation, an adverse event meeting one or more of the following criteria will be handled as a serious adverse event:

- Leading to death.
- Life-threatening.
- Requiring hospitalization or prolongation of hospitalization.
- Leading to permanent and/or significant disability or dysfunction (according to the opinion of the reporting physician).
- Leading to congenital anomaly.
- Other medically major event.

If an adverse event exposes a subject to danger, or requires medical procedures to prevent one of the results defined above, even if the event does not lead to death, is not life-threatening, and does not require hospitalization, it will be handled as a serious adverse event on the basis of appropriate medical judgment.

For example, bronchial asthma which requires intensive therapy at emergency department, etc., vascular disorder or convulsion not requiring hospitalization, drug dependency or abuse are included. In addition, all events meeting the below criterion are taken to be serious adverse events. The principal investigator or sub-investigator will judge the seriousness of adverse events.

- AST and/or ALT >3 times the upper limit of the respective reference values, and total bilirubin >2 times the upper limit of the reference values.

7.7.7.8.2 Reports of serious adverse events

The principal investigator will report the details of all serious adverse events to the sponsor, using the

serious adverse event report form, within 24 hours after the relevant events are judged to be serious. All serious adverse events will be reported, irrespective of the causal relationship with the study drug. The sponsor can also request additional information about serious adverse events.

As far as possible, the principal investigator will report all serious adverse events using the diagnostic names. If the diagnostic name has not been fixed at the time of reporting, the report will state the individual signs and symptoms.

Serious adverse event reports and contact person for reporting
[REDACTED]

If the sponsor judges follow-up to be necessary, the principal investigator will report to the above contact person by fax or email, using a serious adverse event form, and will provide any new information to the sponsor. The principal investigator will evaluate photocopies of relevant documents, such as discharge summaries, medical records from other departments and institutions, and autopsy reports, and will include any relevant information in a supplementary serious adverse event report. The sponsor can also request photocopies of such reports.

The principal investigator will establish appropriate measures for medical treatment of serious adverse events, on the basis of medical judgment. Measures taken with serious adverse events, and their results, will be recorded. The principal investigator will establish the necessary measures, and will also elucidate the causes of serious adverse events as far as possible.

If a serious adverse event during or after the assessment period stipulated in Section 7.7.7.2 is judged by the principal investigator to have a causal relationship with study drug, he will report it to the sponsor.

The principal investigator will also report all serious adverse events to the IRB in accordance with the regulatory requirements. The sponsor will report all reported serious adverse events to the regulatory authority, in accordance with the regulatory requirements.

7.7.7.9 Abuse, misuse, overdose, and medication error (special situations)

In the event of abuse, misuse, overdose, or medication error associated with the study drug (special situations), as defined below, the principal investigator will promptly report it to the sponsor by fax or email, using the form stipulated by the sponsor (Special Situation Report Form). The principal investigator will also submit reports to the sponsor about any serious adverse events associated with the special situation.

- Abuse: Intentional overdose of the study drug, associated with adverse physical or mental effects,

irrespective of whether this is continuous or sporadic.

- Misuse: Inappropriate use of the study drug at doses other than those instructed or on the label, intentionally by the subject.
- Overdose: Accidental or intentional use of the study drug at a dose exceeding that prescribed.
- Medication error: An accidental medication error, including cases that have been prevented from occurring, during the process of prescription, dispensing or administration. A medication error due to the subject forgetting to take one or more doses is not reportable.

7.7.7.10 Pregnancy

The principal investigator or sub-investigator will instruct female subjects that, if they become pregnant during the study, they must stop taking the study drug, and immediately inform the principal investigator or sub-investigator. If a subject is found to be pregnant, the principal investigator or sub-investigator will withdraw her from the study. Information about the pregnancy will be reported to the sponsor as detailed below.

For all pregnancies that occur between initiation of study drug administration and completion of the follow-up period, the principal investigator will send a pregnancy follow-up report to the sponsor by fax or email within 24 hours after the pregnancy comes to light. Pregnancy complications and terminations for medical reasons will be reported appropriately, as adverse events or serious adverse events. Miscarriages will be reported as serious adverse events. In addition, pregnancies will be followed, and pregnancy follow-up reports will be submitted to the sponsor by fax or email. Even after completion of the follow-up period, if a pregnancy comes to light within 1 month after the final study drug administration, the study site will report it to the sponsor. At completion of pregnancy, by birth, miscarriage or termination, the outcome will be reported to the sponsor.

7.7.7.11 Adverse events during study drug administration

Adverse events with onset after the initial study drug administration are taken to be treatment-emergent adverse events (TEAE). For consecutive subjects, of adverse events consecutive from the preceding study at initiation of study drug administration in this study, adverse events that started after initiation of study drug administration in the preceding study are also taken to be TEAEs of this study.

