7.7.7 Evaluation of adverse events

7.7.7.1 Evaluation methods for adverse events

An adverse event is any unfavorable medical event suffered by someone administered a pharmaceutical product (including a study drug) and does not necessarily have a causal relationship with the relevant pharmaceutical product. In other words, an adverse event is any unfavorable and/or unexpected sign (including abnormal laboratory test result), symptom, or disease associated with the administration of a drug, irrespective of any causal relationship with that drug. Surgery that was already planned is not considered to be an adverse event, unless it leads to exacerbation of an existing disease, and is therefore not considered to be a serious adverse event even if it necessitates hospitalization. However, if an additional surgery is performed in connection with the planned surgery, this is taken to be an adverse event, and to be a serious adverse event if prolongation of hospitalization is required, or if any other criterion for being a serious adverse event is met. Hospitalization or prolongation of hospitalization for reasons other than adverse events is not considered to constitute a serious adverse event.

The presence or absence of an adverse event will be confirmed on the basis of the subject's spontaneous complaint, non-inductive questions, examination, C-SSRS, blood pressure, pulse rate, body weight, and ECG or laboratory test results. Adverse events include new onset of an event, increase in the severity or frequency of an event since administration initiation, and diagnostic abnormality, including abnormal laboratory test results. A symptom recorded as a medical history at study initiation will be handled as an adverse event only when symptoms are aggravated. In addition, loss of efficacy, and changes in the primary disease (depression) or scores for any of the CDRS-R items, will not be handled as adverse events in this study, unless judged to be serious adverse events.

The principal investigator or sub-investigator will evaluate adverse events. The principal investigator or sub-investigator will carefully investigate each adverse event, and record in the CRF the date of onset, time of onset, date of cessation (if the outcome is recovery or death), severity, seriousness (including the reason for judging seriousness), causal relationship with the study drug, actions taken for the adverse event, and outcome of the adverse event.

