7.7.7.2 Assessment period

Adverse events occurring between obtaining the legal representative's informed consent (for new subjects) or initiation of study drug administration in this study (for consecutive subjects) and 7 days after the final administration of study drug (the follow-up period) as well as adverse events consecutive from the preceding study at the initiation of study drug administration in this study (only if applicable) will be assessed. For consecutive subjects, adverse events that occurred between obtaining informed consent for this study and initiation of study drug administration in this study will be assessed in the preceding study. In the case of withdrawn subjects, the principal investigator or sub-investigator will assess adverse events up to 7 days after final administration of the study drug. Appropriate follow-up will be continued until one of the following, and the outcome will be determined on that basis: (i) the relevant adverse event recovers to the pre-administration state (if consecutive from the preceding study, it should be recovered to the pre-administration of the preceding study); (ii) the subject's condition stabilizes or becomes chronic; (iii) the subject is lost to follow-up; or (iv) the principal investigator or sub-investigator judges further assessment to be unnecessary. In addition, if the subject stops visiting hospital during the study, he/she will be followed up by an appropriate method such as by telephone, and the findings will be entered in the CRF.

If the above adverse event follow-up has to be continued for 28 days or more after completion of administration, the outcome at the earliest date after 28 days after completion of administration will be recorded in the CRF.

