8.11.1 Adverse events

Adverse events will be classified by system organ class and preferred term, in accordance with MedDRA. Of the adverse events reported using CRFs, TEAEs will be used for safety analysis. TEAEs are defined in Section 7.7.7.11 .

The number of subjects suffering TEAEs, and the numbers suffering death, other serious TEAEs, TEAEs leading to discontinuation of administration, and TEAEs leading to dose reduction will be determined. The TEAE rate and 95% confidence interval will be calculated by the Clopper-Pearson method. The number

of adverse events will also be included. Adverse drug reactions will be summarized in the same manner as TEAEs. Adverse drug reactions are defined in Section 7.7.7.4 .

As summarization of TEAEs by system organ class and preferred term, the number and proportion of subjects suffering these events will be shown. In addition, TEAEs will be summarized by severity, onset timing, and outcome. Adverse drug reactions will be summarized similarly.

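### An event that starts in screening and worsens on duloxetine may or may not be a TEAE, depending on how the site records it; neither the protocol nor the SAP says which

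*Protocol*

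**What the plan says.** Five protocol provisions bear on the point.

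- **What an adverse event is (7.7.7.1):** "Adverse events include new onset of an event, increase in the severity or frequency of an event since administration initiation". For pre-existing conditions: "A symptom recorded as a medical history at study initiation will be handled as an adverse event only when symptoms are aggravated".
- **What is recorded (7.7.7.1):** investigators "record in the CRF the date of onset, time of onset, date of cessation", together with severity, seriousness, causality, action taken and outcome. No date of worsening is listed.
- **When collection starts (7.7.7.2):** from "informed consent (for new subjects) or initiation of study drug administration in this study (for consecutive subjects"). The 1- to 3-week screening period of new subjects is therefore covered.
- **How severity is recorded (7.7.7.3):** "The highest severity of each event during its period of occurrence will be recorded as the severity in the CRF".
- **What is treatment-emergent and analysed (7.7.7.11 and 8.11.1):** "Adverse events with onset after the initial study drug administration are taken to be treatment-emergent adverse events (TEAE"), and "Of the adverse events reported using CRFs, TEAEs will be used for safety analysis". For consecutive subjects, carried-over "adverse events that started after initiation of study drug administration in the preceding study are also taken to be TEAEs of this study".

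SAP 10.1 does not use the term TEAE. It evaluates events that occur from the start of the extension onward and those continuing from the preceding study. It has no rule for worsening.

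**The concern.** Long-term safety is the primary objective, and a symptom that was mild before dosing and becomes severe on drug belongs in that evaluation. The adverse event definition has a worsening limb and the TEAE definition does not. If the worsened event stays in its original record, its onset precedes the first dose and the TEAE filter removes it. The filter also applies to serious TEAEs, TEAEs leading to discontinuation and TEAEs leading to dose reduction, because 8.11.1 counts these among TEAEs.

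Two sites could therefore follow the protocol in good faith and contribute different counts for the same clinical course. The resulting incidence would partly reflect recording habit.

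**Working it through.** **1. Who is affected.** The case needs a new subject whose event (a) starts after consent, (b) is still ongoing at the first dose and (c) increases in severity or frequency afterwards. Complications already present at consent are recorded as medical history (7.2) and become adverse events when aggravated (7.7.7.1), so they are outside the gap. In consecutive subjects, carried-over events that began after the first dose of the preceding study are TEAEs already. Only those that began before that dose raise the same question.

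**2. The same event under two recordings.** Let onset be *d* days before the first dose, with *d* at least 1. SAP 10.1 item 5 computes onset timing as onset date − first dose date + 1.

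| | One record, original onset | New record at the worsening |
|---|---|---|
| Onset after first dose (7.7.7.11) | No | Yes |
| In the TEAE analysis (8.11.1) | No | Yes |
| Onset timing (SAP 10.1 item 5) | −*d* + 1, zero or negative; the first dosing day is day 1 | The interval containing the worsening |
| Dose at onset (SAP 10.1 item 8) | None; dosing had not begun | Dose on the worsening date |

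The left column fits the single highest severity in 7.7.7.3 and the absence of a worsening date from the listed CRF items. The right column fits the worsening limb of 7.7.7.1. No section instructs either.

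**3. Does the SAP settle it?** Its inclusion sentence turns on when an event occurs, so the answer again depends on whether the worsening is a separate event. If the start of the extension were read as consent, all screening events would enter, worsened or not. That would contradict Protocol 8.11.1.

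**4. Denominator.** Protocol 8.2 gives 100 one-year completers and 25% dropout: 100 / (1 − 0.25) = 133.3, rounded up to 134. The stated 135 agrees within rounding (135 × 0.75 = 101.25). I use 135, although the safety set could be smaller if some registered subjects are never dosed.

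**5. What one subject is worth.** 1 / 135 = 0.74 percentage points. Clopper-Pearson 95% intervals:

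- 0/135: 0%, upper limit 2.70%.
- 1/135: 0.74%, upper limit 4.06%.
- 2/135: 1.48% (0.18% to 5.25%).
- 3/135: 2.22% (0.46% to 6.36%).

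The SAP's table of events at 2% or more needs 0.02 × 135 = 2.7, so 3 subjects. Losing one of three takes the event out of that table.

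**6. How many subjects.** The documents give neither the number of new subjects nor any screening event rate, so these inputs are assumptions. Take 35 to 100 new subjects, 10% to 30% with a screening event and 5% to 20% of those worsening on drug:

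- Low: 35 × 0.10 × 0.05 = 0.18 subjects, or 0.13 percentage points of 135.
- High: 100 × 0.30 × 0.20 = 6.0 subjects, or 4.44 percentage points.

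Both ends overstate the loss on these inputs. They leave out the chance that a screening event has resolved before the first dose, and they assume every site keeps a single record. An outer case, with all 135 subjects new and 10% of them affected, gives 13.5; nothing in the documents supports inputs that extreme.

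**The case against.** The best reply is that the sections can be reconciled as they stand. TEAEs are a subset of adverse events. Under 7.7.7.1 an increase since dosing began is itself an adverse event, and such an increase can only begin after the first dose, so it meets 7.7.7.11. On that reading 7.7.7.3 applies to the increase as its own event. The CRF is also completed under separate procedures (9.7.1) that are not among these documents and may contain the convention.

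Most of this stands. A reader might infer that the onset rule necessarily removes every exacerbation from the safety analysis; the text does not support that, because the worsening may be recorded as a new event. Three other inferences also go too far:

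- **That pre-existing illness in general is lost.** The medical-history rule covers it.
- **That the loss falls mainly on moderate and severe events.** The documents contain nothing on this.
- **That the carry-over rule for consecutive subjects is an unfair contrast.** It admits events that began after study drug was started in the preceding study, whereas screening events in new subjects precede any study drug. Treating the two differently is a defensible choice.

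What the reply does not supply is an instruction. The reconciling reading is available but not stated, and the single-severity rule leaves the other one open. Individual reporting of serious adverse events (7.7.7.8.2) is unaffected; the issue concerns the aggregate tables.

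**Conclusion.** The point holds as a gap in definition and recording. An event in a new subject that starts after consent, is ongoing at the first dose and worsens on duloxetine is inside or outside the primary safety tables according to whether the site opens a new record. Neither document decides this.

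The size is unknown. On assumed inputs it runs from well under one subject to about six, before allowing for events that resolve before dosing and for sites that already open a new record. A few subjects at most is a reasonable expectation. That would not change the overall safety picture, but a single subject can matter for a rare event or at the 2% table threshold. The point is worth correcting because it touches the primary objective and the correction is cheap.

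**What to change.** In Protocol 7.7.7.11 and SAP 10.1, define a TEAE as an event with onset after the first dose, or an event present before the first dose whose severity or frequency increases after it. Keep the existing rule for carried-over events in consecutive subjects.

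Add a CRF completion note: a worsening after the first dose is entered as a separate adverse event with the worsening date as its onset, and the pre-dose record keeps the highest severity reached before that date. SAP 10.1 items 5 and 8 can then place the worsening by time and by dose. The note needs to reach sites while events are being recorded, because the listed CRF items contain no worsening date from which to reconstruct it.

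The cost is a sentence in each document and the note, with no added visit or test. The downside is a slightly higher TEAE count.
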